8.4.3.1.2 Causality

Causality (likelihood that the event is caused by the study agents) will be assessed by the PI considering the factors listed under the following categories:

Definitely Related

- reasonable temporal relationship
- follows a known response pattern
- clear evidence to suggest a causal relationship
- there is no alternative etiology

Probably Related

- reasonable temporal relationship
- follows a suspected response pattern (based on similar agents)
- no evidence of a more likely alternative etiology

Possibly Related

- reasonable temporal relationship
- little evidence for a more likely alternative etiology

Unlikely Related

• does not have a reasonable temporal relationship

AND/OR

• there is good evidence for a more likely alternative etiology

Not Related

• does not have a temporal relationship

AND/OR

• definitely due to an alternative etiology

Note: Other factors (e.g., dechallenge, rechallenge, if applicable) should also be considered for each causality category when appropriate. Causality assessment is based on available information at the time of the assessment of the AE. The investigator may revise the causality assessment as additional information becomes available.

Causality assessment will be reviewed by the sponsor. The sponsor may make a separate and final determination on the "reasonable possibility" that the event was "related" (comprising definitely, probably, and possibly related) or "unrelated" (comprising unlikely and not related) to the study agent, in keeping with applicable (US FDA) guidance on sponsor IND safety reporting.

8.4.3.2 Recording of Events

AEs will be promptly recorded in the research database, regardless of possible relationship to study interventions. If a diagnosis is clinically evident (or subsequently determined), the diagnosis rather than the individual signs and symptoms or laboratory abnormalities will be recorded as the AE. The investigator will review events regularly to ensure they have been captured correctly and to perform assessment of events individually and cumulatively to assess possible safety trends.

8.4.3.3 Investigator Reporting Responsibilities

The PI and/or equally qualified designee will check daily for events that may require expedited reporting.

The PI and/or equally qualified designee will also monitor all accumulating data no less than weekly, or according to superseding NIH or NIAID policy, whichever is more frequent.

Data will be reviewed by the PI/designee on a regular basis for accuracy and completeness.

Data will be submitted to the sponsor in keeping with all applicable agreements and when requested, such as for periodic safety assessments, review of IND annual reports, review of IND safety reports, and preparation of final study reports.

The PI and/or other study designee will ensure prompt reporting to safety oversight bodies (e.g., CSO, DSMB), regulatory entities, and stakeholders as specified below, and according to any additional requirements or agreements.

8.4.3.3.1 Adverse Events

Unless otherwise specified above, AE data will be entered into the research database no less than every other week and will include all data through one week prior to database entry. AEs, including laboratory abnormalities, will be followed until resolution or stabilization.

8.4.3.3.2 Serious Adverse Events (Expedited Reporting)

Unless otherwise specified above, all SAEs (regardless of relationship and whether or not they are also UPs) must be reported to the CSO as specified by the CSO (e.g., REDCap system; use the Safety Expedited Report Form [SERF]/email if REDCap is not available). If the preferred/indicated mechanism for reporting is not available, the CSO/SMM should be contacted by telephone, fax, or other reasonable mechanism to avoid delays in reporting.

CSO CONTACT INFORMATION:

Clinical Safety Office [name] [contact]

[contact]

Email: [contact]

REDCap access: https://crimsonredcap.cc.nih.gov/redcap/index.php

Unless otherwise specified above, deaths and immediately life-threatening SAEs must be reported to the CSO promptly, and no later than the **first business day** following the day of study personnel awareness.

All other SAEs must be reported to the CSO no later than the **third business day** following the day of study personnel awareness.

If an individual subject experiences multiple SAEs in a closely timed/overlapping "cause-and-effect" (cascade) sequence, the PI, after careful evaluation, will report ONLY primary/precipitating event(s) individually. SAEs that are determined to be definitely secondary to other SAEs will be detailed in the narrative portion of the report of the relevant primary/precipitating SAE. A clinical rationale and findings to support such reporting should be part of the narrative.

For each SAE report, the research database entry MUST match the corresponding entries on the SAE report (e.g., start and stop dates, event type, relationship, and grade), and **must be updated if necessary** (e.g., if the SAE report was generated after the corresponding AE was entered in the research database).

Unless otherwise specified above, SAEs that have not resolved by the end of the per-protocol follow-up period for the subject are to be followed until final outcome is known (to the degree permitted by the IRB-approved informed consent form). If it is not possible to obtain a final outcome for an SAE (e.g., the subject is lost to follow-up), and to update the CSO, the last known status and the reason a final outcome could not be obtained will be recorded by the investigator on an SAE report update and in CRIMSON.

8.4.3.3.3 Unanticipated Problems

Unless otherwise specified above, UPs (as defined in this protocol, or as defined by the IRB of record, whichever definition is more conservative) that are also AEs or SAEs, must be reported to the CSO (by REDCap, or by email and SERF if REDCap is not available) no later than when they are due to be reported to the IRB.

UPnonAEs are NOT reported to the CSO but must be reported to the Clinical Trials Management (CTM) group and the IRB according to their requirements and preferred methods. If the UPnonAE raises a significant potential subject safety concern, the SMM should be consulted by email or phone no later than when reports are made to the IRB and/or CTM and provide details of the UPnonAE.

8.4.3.3.4 Pregnancy

Unless otherwise specified above, all pregnancies will be reported (by REDCap, or by email and SERF if REDCap is not available) to the CSO no later than the first business day following the day of study personnel awareness.

Pregnancy outcome data (e.g., delivery outcome, spontaneous or elective termination of the pregnancy) will be reported to the CSO no later than the third business day following the day of study personnel awareness (by REDCap, or by email and SERF if REDCap is not available).

Pregnancy itself is not an AE. Events that meet AE or SAE criteria in relation to pregnancy, delivery, or the conceptus/neonate (see section 8.4.1) are reportable (by REDCap, or by email and SERF if REDCap is not available).

In the event of pregnancy in a study subject exposed to study agent, the following actions will be taken, with the goal of ensuring maternal and fetal well-being, in consultation with the SMM and DSMB:

- Discontinue the following study-specific procedures:
 - Collection of whole blood (peripheral blood mononuclear cells [PBMC] and PAXgene for RNA) and serum for research testing.
 - Nasal SAM.

- Nasal brushing.
- Continue to follow for safety for the duration of the pregnancy.
- Request to unblind the subject, if applicable, AND if doing so would offer a benefit to the subject.
- Report, no later than the first business day after study personnel awareness, to the DSMB and/or the IRB.
- Advise subject to notify the obstetrician of study participation and study agent exposure, providing contact information for the obstetrician to contact the study PI, should this be required, and with the subject's consent.

8.4.3.4 Sponsor's Reporting Responsibilities

Events reported to the sponsor will be promptly evaluated and will be reported as required according to FDA IND safety reporting guidance and regulations. IND safety reports will be sent to other investigators conducting research under the same IND and will be shared with other stakeholders according to applicable agreements.

The sponsor will also submit an IND annual report of the progress of the investigation to the FDA as defined in 21 CFR 312.33.

All UPs will be evaluated by the sponsor, and a summary of the event, and any necessary (corrective/preventative) actions, will be distributed to investigators conducting research under the same IND as may be relevant and appropriate.

8.4.4 Withdrawal Criteria for an Individual Subject

An individual subject will be withdrawn from the study for any of the following:

- An individual subject's decision. (The investigator should attempt to determine the reason for the subject's decision.)
- Non-compliance with study procedures to the extent that it is potentially harmful to the subject or to the integrity of the study data.
- A change in the subject's condition as follows:
 - At the PI's discretion, development of any condition so that the participant no longer meets one or more of the eligibility criteria.
- The investigator determines that continued participation in the study would not be in the best interest of the subject.

Participants may withdraw prior to vaccine administration and no further testing or follow-up will be performed. The PI or designee will discuss with the participant why she/he wants to prematurely withdraw from the study to determine the best course of action for the participant. If the participant would like to withdraw after vaccination, clinical laboratory tests and procedures for safety purposes will continue as obtainable and at a frequency determined by the PI. If the participant does not return for scheduled follow-up visits, the study staff will make every

reasonable effort to contact the participant by phone, mail, or email, or a combination of the three and reiterate that follow-up visits are strongly encouraged for safety reasons.

8.4.4.1 Re-enrollment and Unplanned Procedure Repetition

Unless otherwise specified within this protocol, each person who is a subject in this study may be enrolled, and may pass through each step and process outlined in the protocol, only **ONCE** (i.e., subjects may not "go back" and repeat a protocol step already completed). On a case-by-case basis, a request for re-enrollment, or for repetition of a protocol step or procedure already completed, may be submitted to, reviewed by, and approved by the SMM in writing. The SMM may also recommend or require consultation of the IRB and/or DSMB.

8.4.4.2 Replacement of Withdrawn Subjects or Subjects Who Discontinue Study Agent

A participant who withdraws before study agent administration will be removed, and no data will be used in the safety or efficacy analysis or publication of the study. If this occurs, another participant from the over accrual may be added and randomized to a trial arm.

Additional participants from the over accrual may also be added to compensate for participants who withdraw or are lost to follow-up after study vaccine administration on V_1D0 but before the V_2D7 visit.

All subjects exposed to study agents will be included in the safety dataset.

8.4.5 Additional Safety Oversight

8.4.5.1 Safety Review and Communications Plan

A safety review and communication plan (SRCP) is required for this protocol. The SRCP is an internal communications document between the PI and the CSO, as sponsor representative, which delineates key safety oversight responsibilities of the PI, the CSO, and other stakeholders. The SRCP includes a plan for conducting periodic safety surveillance assessments by the CSO.

8.4.5.2 Sponsor Medical Monitor

A SMM, representing the sponsor, has been appointed for oversight of safety in this clinical study. The SMM will be responsible for performing safety assessments as outlined in the SRCP.

8.4.5.3 Oversight Committees

8.4.5.3.1 Data and Safety Monitoring Board

The NIAID intramural DSMB includes independent experts that do not have direct involvement in the conduct of the study and have no significant conflicts of interest as defined by NIAID policy. The DSMB will review the study protocol, consent document, and investigator brochure prior to initiation and at least once a year thereafter, or at a frequency determined by the DSMB.

The DSMB may convene additional reviews as necessary. The DSMB will review the study data as needed to evaluate the safety, efficacy, study progress, and conduct of the study.

All deaths, SAEs, UPs, pregnancies, and IND safety reports will be reported to the DSMB at the same time they are submitted to the IRB and CSO unless otherwise specified herein. A summary of PSEEs will also be provided for review by the DSMB along with study documents submitted for periodic scheduled DSMB reviews.

All cases of intentional or unintentional unblinding will be reported to the DSMB not later than one business day from the time of study personnel awareness.

The PI will notify the DSMB at the time pausing or halting criteria are met and obtain a recommendation concerning continuation, modification, or termination of the study. The PI will submit the written DSMB summary reports with recommendations to the IRB.

8.4.6 Pausing Rules for the Protocol

"Pausing" is discontinuation of study intervention/treatment/dosing (agent/placebo/procedure, etc) in a protocol-defined dose group or "arm" at the discretion of the sponsor until a decision is made to either resume or permanently discontinue such activity. The IM or IN route of study agent administration may be paused at the discretion of the DSMB who will not be blinded. The investigators will continue to be blinded as to which study arm is paused. Subjects will continue to be followed for safety during a pause.

The pausing criteria for a group of subjects in this study include any one or more of the following:

- A subject experiences an SAE that is unexpected (per the investigator's brochure or product label) and possibly, probably, or definitely related to a study agent or route of administration;
- A subject experiences two grade 3 or greater AEs that are unexpected (per the investigator's brochure or product label) and possibly, probably, or definitely related to a study agent or route of administration.

The PI or the CSO may also pause dosing/study interventions for one or more subjects for any safety issue. The DSMB may recommend a pause to the CSO.

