6.1.2 Dosing and Administration

A single study agent dose of 1 mL will be used either IM or given in two doses of 0.5 mL IN in each nare. Participants will be randomized to receive IM and IN doses of study agents twice 28 days apart as follows:

- Group A: IM BPL-1357 and IN placebo.
- Group B: IM placebo and IN BPL-1357.
- Group C: IM and IN placebo.

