6.1.3 Drug Administration

Participants will be administered study agent via IM and IN routes by study staff or personnel trained to administer the vaccine.

Participants will receive IM BPL-1357 or placebo in the arm per standard methods. A 1- to 1.5-inch 22G-25G needle as appropriate will be attached to the syringe and 1 dose will be administered in the deltoid muscle of the upper arm. Doses will be given within 4 hours of preparation. Used syringes will be disposed of in biohazard trash, which is handled according to site biohazard trash guidelines.

Participants will receive IN BPL-1357 or placebo using a syringe with nasal atomizer. Participants will be asked to lie down with their heads in a neutral to slightly tilted back position. Two MAD Nasal (Teleflex Incorporated) intranasal mucosal atomization devices will be attached to 2 syringes and 1 half-dose will be administered in each nostril.

[figure not shown]

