7 STUDY INTERVENTION DISCONTINUATION AND PARTICIPANT DISCONTINUATION/WITHDRAWAL

7.1 DISCONTINUATION OF STUDY INTERVENTION

Study intervention may be discontinued for a single route (i.e., pausing), or it may be discontinued for all participants and enrollment suspended (i.e., halting). Pausing and halting rules and procedures are described in sections **Error! Reference source not found.** and 8.4.6.

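### The protocol promises that investigators stay blind to which arm is paused, but it defines a pause in conflicting ways and describes no masking for any of them

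*Combined protocol and SAP*

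**What the plan says.** Three statements about a pause have to fit together.

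- Section 7.1 makes the unit a route: "Study intervention may be discontinued for a single route (i.e., pausing".
- Section 8.4.6 first makes the unit an arm, with placebo stopping too: "discontinuation of study intervention/treatment/dosing (agent/placebo/procedure, etc) in a protocol-defined dose group". It then returns to the route: "The IM or IN route of study agent administration may be paused at the discretion of the DSMB who will not be blinded".
- Section 8.4.6 adds the promise: "The investigators will continue to be blinded as to which study arm is paused".

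The dosing is double-dummy. Section 6.1.2 says "Participants will be randomized to receive IM and IN doses of study agents twice 28 days apart as follows", and all three groups then have both an IM and an IN component. Section 6.1.3 says who gives the doses: "Participants will be administered study agent via IM and IN routes by study staff or personnel trained to administer the vaccine". Under 6.3.2 the participants, clinical staff and study team are blinded. The pharmacist who prepares the syringes is not (6.3.1).

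The investigator grades severity (8.4.3.1.1). The PI assigns causality, which may be revised later (8.4.3.1.2). Under 9.4.2, one related SAE in an arm is enough for that arm's primary safety endpoint to be met.

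**The concern.** In a trial where each group used a single route, pausing a route and pausing an arm would be much the same act. Here they differ, because all three groups use both routes. Pausing a route touches every group, including those receiving saline by that route. Pausing an arm touches only that group, by both routes. Each act is visible where doses are given, and each shows something different.

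The primary comparison depends on judgements of severity and relatedness. Section 4.2 relies on double blinding to keep bias out of it, and scheduled unblinding comes only after the last V2D182 visit (6.3.3). If a pause gives assessors information about allocation, later grading, and revision of earlier causality calls, are no longer fully masked, although the protocol says they are. Relatedness also drives the pausing and halting rules, and the PI takes part in the decision on resumption (8.4.6.2).

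**Working it through.** **1. How likely is a pausing trigger?** Inputs: 15 participants per arm and true rates of 5%, 10% and 15% (section 9.2, Table 8). The chance that an arm meets a criterion is a = 1 − (1 − p)^15.

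- 5%: 1 − 0.4633 = 0.537
- 10%: 1 − 0.2059 = 0.794
- 15%: 1 − 0.0874 = 0.913

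These reproduce Table 8.

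**2. How likely is it that only one vaccine arm triggers?** Section 9.2 says that criteria met in both arms amount to a halt, so the relevant quantity is exactly one arm: 2a(1 − a). Assumption: both vaccine arms share the same true rate. Timing is ignored.

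- 5%: 2 × 0.5367 × 0.4633 ≈ 0.50
- 10%: 2 × 0.7941 × 0.2059 ≈ 0.33
- 15%: 2 × 0.9126 × 0.0874 ≈ 0.16

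Below the range of Table 8, the same formula gives 0.24 at 1% and 0.39 at 2%. All these rates are hypothetical; the protocol predicts none of them.

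**3. What does each form of pause show to blinded staff?** Before a pause, any participant has a 30/45 = 0.67 chance of being on active vaccine.

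| Form of pause | What staff can see | What it reveals |
|---|---|---|
| All dosing stopped in one arm | Which participants with doses pending are not dosed | Those participants share an arm. If only a vaccine arm would be paused (assumption), their chance of active vaccine becomes 1.00 and that of continuing participants 15/30 = 0.50. If any arm were equally likely to be paused, both stay at 0.67. A versus B is not shown directly. |
| One route stopped for everyone | Which route has stopped | The implicated vaccine arm (IM is A, IN is B), and a pointer to the triggering participant. Other participants stay at 1/3 for each group. |
| One route stopped only in the arm receiving active by it | Who misses which route | That arm is fully unblinded. |
| Active replaced by saline in the pharmacy | Nothing | Nothing, but the protocol does not describe this. |

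**4. Is masking described anywhere?** Section 6.3.4 deals with unintentional unblinding after it has happened. Section 10.8.1 says in general terms that potentially unblinding data will be handled with special care. Neither says how a pause is concealed, or provides an assessor separate from the dosing clinic.

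**The case against.** The strongest reply is that section 8.4.6 promises only blindness to which arm is paused, not blindness to every clue. An arm pause does not by itself tell staff whether the arm is A or B. A route pause leaves almost all individual allocations unknown. The unblinded pharmacist prepares the syringes, so a concealed substitution is possible and double-dummy dosing does not in itself make a stop visible. A halt stops everyone and shows no arm, and a pause with no doses pending shows nothing at the clinic. All of this stands, and it limits the point. It does not supply the missing mechanism: the 8.4.6 definition stops agent and placebo alike, and a route pause carried out that way shows exactly what the sentence says stays hidden.

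A reader might infer more than the documents support:

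- *That any pause lets assessors sort all participants by arm.* Only an arm-level stop does this, and only for participants with doses pending; 15 of 45 is a ceiling on those seen to stop.
- *That a local nose or arm reaction gives the arm away.* Everyone receives both routes, and section 2.3.1.2 lists local reactions to saline by each.
- *That a damaging pause has probability 0.79 at 5% or 0.99 at 15%.* Those are the chances that at least one vaccine arm triggers. They include both arms triggering, which section 9.2 equates with a halt.
- *That participants would go on being randomized into a paused arm.* Sections 7.1 and 8.4.7 tie suspension of enrollment to a halt, but no text orders randomization to continue during a pause, and 8.4.6.2 allows further requirements to be set. This is a silence to fill, not a stated rule.

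**Conclusion.** The point holds in a limited form. Sections 7.1 and 8.4.6 disagree on the unit of a pause, and the promise that investigators remain blind has no described means behind it. Carried out as written, a pause reveals allocation information to the people who grade and attribute AEs. How much depends on the form of the pause and on how many doses are pending. It is not a general unblinding of the trial.

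The probabilities of about 0.50, 0.33 and 0.16 rest on equal rates in the two vaccine arms. They ignore timing: a pause may precede a halt, and further events in the same arm may turn a pause into one. They also count criteria met, whereas 8.4.6 leaves the pausing of a route to the DSMB's discretion. They show that a one-arm trigger is a realistic event to plan for, not a forecast.

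**What to change.** - Reconcile sections 7.1 and 8.4.6 to one unit of pausing. The clinical form of the pause is for the sponsor and DSMB to decide.
- State how a pause is masked from those who grade and attribute AEs. If it cannot be masked, withdraw or qualify the sentence that investigators remain blinded.
- Record the pause date and keep an audit trail of severity and causality as assessed before it. This must not delay the pause, and later updates to causality and SAE reports continue as planned.
- Also report the V2D28 and V2D182 AE comparisons restricted to AEs with onset before the pause, using the pre-pause assessments. Mark any such event that was first assessed after the pause.
- Say whether randomization continues during a pause.

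The cost is protocol wording, an audit trail and one extra table. The pre-pause analysis will have fewer events and less precision, so it supplements the planned comparison and does not replace it. No sample size or power figure changes.
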